## **7. STUDY POPULATION**

### **7.1. Enrollment by Investigator**

Enrollment by geographic region (North America, Europe, Asia/Pacific, and Other), country, and investigator will be summarized.

### **7.2. Subject Disposition and Completion Status**

The subject disposition summary will include the counts and percentages of subjects who:

- Completed study treatment
- Discontinued study treatment early, overall and by reason for not completing study treatment
- Completed the study
- Discontinued from the study early, overall and by reason for not completing the study

The subject disposition listing will include the date the informed consent form was signed, dates of first dose and last dose of study drug, primary reason for discontinuation of study treatment, and primary reason for study discontinuation. (If the treatment and study discontinuation reasons are the same for all subjects, as expected, a single column with the heading “Primary Reason for Discontinuation” may be shown.) A listing of premature discontinuation for reasons other than termination of the study by the sponsor will also be provided.

### **7.3. Protocol Deviations**

A subject listing of all protocol deviations identified prior to database lock will be provided.

### **7.4. Medical History and Medical Conditions Present at Entry**

Medical history will be summarized by system organ class and preferred term. Medical history will be mapped according to [REDACTED]

### **7.5. Demographic and Baseline Clinical Characteristics**

A summary of demographic and baseline characteristics will include the following: age (years), age category (< 65 years, ≥ 65 years), sex, race, ethnicity, weight (kg), height (cm), BMI (kg/m^2), and diagnosis of primary autonomic failure (Multiple System Atrophy, Parkinson’s Disease, Pure Autonomic Failure). In addition, a summary of previous treatment during the Study 0170 randomized withdrawal period and a listing of previous treatment during the Study 0170 randomized withdrawal period and (if applicable) previous treatment during Study 0169 will be provided.

## 8. SAFETY AND TOLERABILITY

Safety and tolerability summaries include an overall summary of adverse events and summaries of drug exposure (duration of treatment), dosing information/compliance, concomitant medications, clinical laboratory results, vital signs, ECGs, incidence of falls/near-falls, C-SSRS responses, and [REDACTED]

### 8.1. Adverse Events

Adverse events are collected from signing of the informed consent form through the end of the study. Adverse events will be coded to the preferred terms of the Medical Dictionary for Regulatory Activities (MedDRA®, version 24.1).

A treatment-emergent adverse event (TEAE) will be defined as any AE that begins on or after the date of first dose of Study 0171 study drug up through 14 days after the date of last dose of study drug. AEs that begin more than 14 days after the date of last dose of study drug and AEs that begin during the period from obtaining informed consent to the start of administration of study drug will not be considered treatment-emergent and will be listed only.

The following AE summaries will be provided:

- TEAE overall summary
- TEAEs by preferred term
- TEAEs by system organ class and preferred term
- Moderate or severe TEAEs by system organ class and preferred term
- TEAEs by preferred term with frequency > 3% of safety analysis set subjects
- TEAEs by system organ class, preferred term, and severity
- Drug-related TEAEs by system organ class and preferred term
- Drug-related TEAEs by system organ class, preferred term, and severity
- Drug-related moderate or severe TEAEs by system organ class and preferred term
- Serious TEAEs by system organ class and preferred term
- Drug-related serious TEAEs by system organ class and preferred term
- TEAEs resulting in on-study deaths
- TEAEs leading to premature study drug discontinuation
- TEAEs leading to temporary interruption of study drug
- TEAEs of special interest by system organ class and preferred term (Section 8.1.1)

If no adverse events meeting a specific table definition were reported, the body of the table will contain only a statement that no events met the table definition.

The following AE listings will be provided:

- TEAEs
- AEs leading to premature study drug discontinuation
- AEs resulting in temporary interruption of study drug
- Serious adverse events
- Deaths
- Non-treatment-emergent adverse events

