### 8.5.1. [REDACTED]

### 8.5.2. Adverse Event Data

Adverse events will be coded to the preferred terms of the Medical Dictionary for Regulatory Activities (MedDRA®). Summaries will present by system organ class (SOC), preferred term (PT) and severity, the frequency and percentage of subjects reporting each observed event.

A treatment-emergent adverse event (TEAE) will be defined as any AE that begins on or after the date of first dose of study drug up to the date of last dose of study drug plus the number of days in the follow-up period.

The number and percentage of subjects who experience TEAEs will be summarized. Summaries of TEAEs will include the following:

- [REDACTED]
- [REDACTED]
- [REDACTED]

[REDACTED]

[REDACTED]

[REDACTED]

[REDACTED]

[REDACTED]

All AEs reported will be listed by subject. A listing will be provided for all subjects who experience an SAE. Listings will also be provided for subjects who discontinued study treatment prematurely because of AEs and subjects who temporarily interrupted study treatment because of AEs. The AESIs, as described in Section 7.1.4 will be listed and summarized.

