## **2. INTRODUCTION**

This document describes the plan for the summarization and analysis of clinical data collected in Study 0171 for TD-9855, which was terminated early by the sponsor with 110 subjects enrolled.

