### **3. STUDY OBJECTIVES AND ENDPOINTS**

#### **3.1. Objectives**

##### **3.1.1. Primary Objective**

The primary objective of the study is to evaluate the long-term safety of TD-9855 over a 182-week period.

[REDACTED]

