## **5. TIMING OF PLANNED ANALYSES**

The primary analysis was to occur when all subjects had completed the [REDACTED] and the database had been cleaned and locked. A final analysis was to be conducted when all subjects had completed the study through Week 184.

The study was terminated early by the sponsor and a single analysis of all data obtained is to be conducted instead, after the database has been cleaned to the extent possible and locked.

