### **8.1.1. Adverse Events of Special Interest**

An AE of special interest (AESI) is one of scientific and medical interest specific to understanding the investigational product and may require close monitoring and rapid communication by the investigator to the sponsor. The following are the AESIs defined for the study:

- Supine Hypertension
- Myocardial Infarction
- Cerebrovascular Accident
- Cardiac Arrhythmia
- Congestive Heart Failure
- Convulsion

The incidence of treatment-emergent AESIs will be summarized, overall (any AESI) and by system organ class and preferred term. A listing of AESIs will be provided.

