## 8.7. Incidence of Falls

The numbers and percentages of subjects with at least one fall during the interval beginning on Study Day 1 and ending on Day 189 (the end of the Week 26 analysis window) will be provided, together with the corresponding numbers and percentages of subjects with at least one fall or near-fall.

In addition, the following categorical summaries with counts and percentages will be provided for falls and falls + near-falls:

- None
- 1
- 2
- 3 or more

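### After early termination the AE and AESI tables remain head counts; adding exposure-adjusted rates is a cheap improvement, not the correction of an error

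*SAP*

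**What the plan says.** The SAP Introduction describes a study "which was terminated early by the sponsor with 110 subjects enrolled". SAP Section 5 replaces the planned primary and final analyses: "a single analysis of all data obtained is to be conducted instead". The primary objective (SAP 3.1.1) is to "evaluate the long-term safety of TD-9855 over a 182-week period".

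SAP 8.1 counts an AE as treatment-emergent from the first Study 0171 dose "up through 14 days after the date of last dose of study drug". It then lists 15 AE summaries, by preferred term, system organ class, severity, relatedness, seriousness or consequence. The only measure named in that list is the cut-off "TEAEs by preferred term with frequency > 3% of safety analysis set subjects". Protocol 8.5.2 agrees: "The number and percentage of subjects who experience TEAEs will be summarized". For AESIs, SAP 8.1.1 says: "The incidence of treatment-emergent AESIs will be summarized, overall (any AESI) and by system organ class and preferred term".

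Exposure in days is summarized separately in SAP 8.2 and is not linked to the AE tables. SAP 8.3 does express midodrine use per 28 days of treatment, so the SAP already contains one time-adjusted rate. For falls, SAP 8.7 gives "The numbers and percentages of subjects with at least one fall during the interval beginning on Study Day 1 and ending on Day 189", with categories of none, 1, 2 and 3 or more.

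**The concern.** A percentage of subjects with an event depends on how long each subject was watched. Here the window is subject-specific by definition, and follow-up was cut short by the sponsor. The same n(%) can therefore rest on very different amounts of observation, and a reader asking about long-term safety cannot see from the table how much time supports it.

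Detection also changes during the study. Contacts fall every 4 weeks from Week 2 to Week 26 and every 12 weeks from then to Week 182 (Protocol Tables 1 and 2). Scheduled vital signs, ECGs and laboratory tests stop after Week 26 (Protocol 3.1). A single pooled percentage mixes these two regimes.

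What is at stake is how interpretable a descriptive single-arm report is. No test or between-arm comparison depends on it.

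**Working it through.** The documents state no event count, total person-time or follow-up distribution, so there is no planned figure to reproduce. The safety-set size is not given either; 110 is its upper bound. Every follow-up length in steps 2 to 5 is an assumption.

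**1. Range of the TEAE window by design.** One dose gives 1 + 14 = 15 days. Full treatment gives 182 × 7 + 14 = 1,288 days (3.53 years). The ratio is 1,288 / 15 = 85.9. This is what the definition allows, not the spread that occurred.

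**2. One percentage, several rates.** Take 3 of 110 = 2.7%, with person-time 110 × mean follow-up and exact Poisson limits χ²(0.025; 2k)/(2PY) and χ²(0.975; 2k+2)/(2PY), k = 3.

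| Mean follow-up (years) | Subject-years | Rate per 100 subject-years (95% CI) |
|---|---|---|
| 0.5 | 55 | 5.5 (1.1–15.9) |
| 1 | 110 | 2.7 (0.6–8.0) |
| 2 | 220 | 1.4 (0.3–4.0) |

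**3. One rate, several percentages.** At a constant 5 per 100 subject-years, the expected percentage is the mean of 1 − exp(−0.05 × window in years). It is 2.6% if all windows are 196 days (182 + 14), 3.8% if uniform over 15–560 days, 8.4% if uniform over 15–1,288 days, and 16.2% if all are 1,288 days. Subjects with an event divided by time to first event or end of window returns 5.0 in each case.

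**4. The >3% table.** 3/110 = 2.7% and 4/110 = 3.6%, so a term needs at least 4 subjects. At a true 4 per 100 subject-years, P(X ≥ 4) with X ~ Bin(110, 1 − exp(−0.04t)) is 18%, 63% or 97% at t = 0.5, 1 or 2 years. The term still appears in the full preferred-term tables.

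**5. Does the separate exposure summary suffice?** With follow-up uniform over 0 to T years, subjects with event / (n × mean exposure) has expectation [1 − (1 − e^(−rT))/(rT)] / (T/2).

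| True rate per 100 subject-years | T = 1 | T = 2 | T = 3.53 |
|---|---|---|---|
| 6.4 | 6.3 | 6.1 | 5.9 |
| 30 | 27.2 | 24.8 | 21.7 |
| 100 | 73.6 | 56.8 | 41.1 |

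The shortcut is adequate for rare events. It is not for common ones such as any TEAE, because time after the first event stays in the denominator.

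**6. Why time at risk needs care.** Fourteen unobserved or event-free days add 7.7%, 3.8% or 1.9% to a mean time at risk of 0.5, 1 or 2 years. Two cases arise. A subject lost before last dose + 14 days is not observed for all of that time. After the last dose, almost no TEAE can still lead to stopping the drug.

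**7. Falls.** The window is capped at Day 189. Suppose the Day 182 risk is 50%, so h = ln 2 / 182 per day, and a fraction f leaves uniformly before Day 175. The observed percentage is 0.5(1 − f) + f[1 − (1 − e^(−175h))/(175h)]: 50.0%, 47.7%, 45.4% or 40.8% for f = 0, 10%, 20% or 40%. The effect appears only under assumed dropout.

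**The case against.** The strongest reply is that nothing is lost. SAP 8.1 plans a by-subject TEAE listing, SAP 7.2 lists first and last dose dates, Protocol 8.1 says individual data will be listed, and Protocol 7.3 has onset dates recorded. Time to first event can be rebuilt from these for common as well as rare events. This stands: a reader might infer that rates cannot be recovered, and the documents do not support that. What remains is that rebuilding is the reader's own re-analysis, while the tables a reader normally uses carry no rate.

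A second reply is that the study is single-arm and descriptive, and that the >3% entry is only a display cut-off. This also stands. A reader might infer biased or invalid percentages, but they correctly describe what was observed, and SAP 8.1 does define the observation window.

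Third, SAP 6.1.3 drops subgroup summaries because the sample is too small, and a period split looks contrary to that. A split by time is not a subgroup of subjects, but intervals will be wide.

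Fourth, subjects come from Study 0170 and some from Study 0169, so a clock starting at the first Study 0171 dose does not measure total drug exposure. That is a real limit on comparison with other exposure data.

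Finally, parts of Protocol 8.5.1, 8.5.2 and 8.6 and of SAP Sections 6, 8 and the material after Section 9 are redacted and could hold a related rule. The visible list in SAP 8.1 shows no gaps.

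**Conclusion.** The point holds as a cheap improvement to SAP 8.1 and 8.1.1, with medium confidence. The visible AE and AESI outputs give no time-based measure, although the window varies by subject, the study was stopped early and the objective is long-term safety.

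The size is not known. The 15 to 1,288 days is a design range, and nothing shows that any subject came near the upper end. The illustrations rest on assumed follow-up, a constant event rate and 110 subjects in the safety set.

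Falls are a minor matter. A reader might infer that the falls percentages need a rate per diary day. The window is fixed, the effect depends on assumed dropout, and Protocol Appendix 6 describes paper diaries. No text shows that daily entries reach the database.

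**What to change.** Keep n(%). In SAP 8.1 and 8.1.1 add exposure-adjusted incidence rates per 100 subject-years, with exact 95% confidence intervals, for any TEAE, serious TEAEs, TEAEs leading to study drug discontinuation, deaths and any AESI.

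- **Time at risk:** from first dose to the earliest of first event, last dose + 14 days, death or last contact.
- **TEAEs leading to discontinuation:** time ends at the first such event or, for subjects without one, no later than last dose.
- **Events reported after last contact but inside the TEAE window:** extend that subject's time at risk to the onset date. Protocol 7.4.2 allows related SAEs to be reported for 30 days after last contact, so this can occur.
- **Periods:** overall, Day 1–189, and from Day 190. The first period's time is cut at Day 189. Every subject still under observation enters the second period at Day 190 regardless of earlier events, and the first event in that period is counted.

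For SAP 8.7, an optional addition is the number of subjects whose falls diary ended before Day 175, when the Week 26 window opens. Day 189 would not serve, because a diary returned on time at Visit 6 usually ends before then. Add a rate per diary day only if daily entries are in the database.

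The cost is SAP wording and a few columns from dose, AE and contact dates already collected. The drawbacks are wide intervals with at most 110 subjects, an approximately constant-rate assumption within each period, and a clock that excludes exposure in earlier studies.

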### **8.1.1. Adverse Events of Special Interest**

An AE of special interest (AESI) is one of scientific and medical interest specific to understanding the investigational product and may require close monitoring and rapid communication by the investigator to the sponsor. The following are the AESIs defined for the study:

- Supine Hypertension
- Myocardial Infarction
- Cerebrovascular Accident
- Cardiac Arrhythmia
- Congestive Heart Failure
- Convulsion

The incidence of treatment-emergent AESIs will be summarized, overall (any AESI) and by system organ class and preferred term. A listing of AESIs will be provided.

### **8.2. Extent of Exposure and Treatment Compliance**

Duration of study drug exposure (days) will be summarized. Duration of exposure to study drug is calculated as (date of last dose – date of first dose + 1).

Subjects will take their assigned study medication once daily.

Treatment compliance as a percentage of the expected total dose will be calculated as follows, using the information captured on the CRF page for “Study Drug Dispensing / Return”:

$$100 \times \frac{\text{(number of tablets dispensed – number returned)}}{\text{(date of last dose – date of first dose + 1)}}$$

Treatment compliance as a percentage of expected total dose over the interval from first to last dose will be summarized as a continuous variable and using the following categories, after rounding to the nearest 0.1%:

- $\geq 120\%$
- $\geq 80\% - < 120\%$
- $< 80\%$

Study drug administration (date/time and study day) and drug accountability data will be listed.

### **8.3. Concomitant and Other Medications**

Medications will be coded using the World Health Organization Drug Dictionary (WHODD, version 1Q 2021 C3). Medications entered on the case report form will be mapped to Anatomic Therapeutic Chemical (ATC) drug class and generic drug name. Each verbatim name will be classified by anatomical main group (ATC level 1), therapeutic subgroup (ATC level 2), pharmacological subgroup (ATC level 3), chemical subgroup (ATC level 4), and preferred name (ATC level 5, chemical substance).

Prior medications are medications taken before the first dose of study drug. Concomitant medications are medications taken after the first dose up through 14 days after the last dose, and include ongoing prior medications.

The number and percentage of subjects receiving prior medications, the number and percentage receiving concomitant medications, and the number and percentage receiving prohibited concomitant medications will be summarized by medication class and standardized medication name (preferred name). If available, ATC level 4 will be used to determine the medication class. If ATC level 4 is not available, the next available level of ATC code (i.e., level 3, level 2, or level 1) will be used. Subjects reporting use of more than one medication at each level of summarization (any medication received, ATC class, and preferred name) will be counted only once.

All medications will be listed.

On-treatment midodrine usage will be summarized by providing a categorical summary of number of uses and descriptive summaries (n, mean, SD, etc.) of usage rate (uses/month),

calculated as (number of uses)/(treatment period duration in days, divided by 28) and total dose (mg). For number of uses, counts and percentages will be provided for the following categories:

- 0
- 1
- 2
- 3
- 4
- 5
- 6 – 10
- 11 – 20
- > 20

A use is defined as taking 1 or more 2.5-mg midodrine tablets on a single occasion, e.g., 2 tablets taken at 0900 and 2 tablets taken at 1200 would be counted as 2 uses, for a total daily dose of 10 mg.

#### 8.4. Laboratory Data

Laboratory data hematology and serum chemistry summaries will include summary statistics for observed values and for changes from baseline at each postdose visit. In addition, changes from baseline for each visit relative to normal ranges (e.g., shifts from normal to abnormal high/low) will be summarized in shift tables for hematology and serum chemistry test results. (Urinalysis data will be listed only.)

Listings will flag laboratory values that are outside the normal range.

#### 8.5. Vital Signs

Vital sign (HR, systolic and diastolic BP, respiratory rate, and body temperature) values and their changes from baseline at each visit will be summarized. If baseline BP and HR were collected as a part of the orthostatic standing test at Visit 9 (Day 155) in Study 0170, the seated values will be used to calculate the change from baseline. The counts and percentages of subjects with vital signs in the following categories will be presented in a vital signs extreme values summary. Extreme values will be flagged in the listing.

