**8.5.5. Vital Signs Data**

Vital Signs data will be summarized in terms of observed values (by time point), changes from baseline (by time point), and counts and percentages within appropriately defined categories (Table 3).

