**Table 3: Outlier Threshold for Vital Signs**

Heart Rate (bpm)	Systolic Blood Pressure (mmHg)	Diastolic Blood Pressure (mmHg)
<40	<85	<45
>110	>160	>100

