**Table 5: Vital Signs Thresholds**

Heart Rate (bpm)	Systolic Blood Pressure (mmHg)	Diastolic Blood Pressure (mmHg)
< 40	< 85	< 45
> 110	> 160	> 100

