### Categorical ECG Summary

The number of subjects with absolute ECG values and changes from baseline in the ranges shown in [Table 6](#) will be presented by visit.

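### SAP Table 5 counts vital signs by absolute limits only, so a large blood-pressure rise that ends at or below 160/100 mmHg falls in no vital-sign category and is not flagged

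*SAP*

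**What the plan says.** SAP 8.5 plans two summaries of vital signs. The first is continuous: "values and their changes from baseline at each visit will be summarized". The second is categorical: "The counts and percentages of subjects with vital signs in the following categories will be presented in a vital signs extreme values summary". The categories are those of SAP Table 5, whose only columns are "Heart Rate (bpm) Systolic Blood Pressure (mmHg) Diastolic Blood Pressure (mmHg"), with upper limits "> 110 > 160 > 100" and lower limits of 40, 85 and 45. There is no change-from-baseline column. The listing flags values beyond these limits.

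The protocol plans the same. Its section 8.5.5 promises observed values, "changes from baseline (by time point), and counts and percentages within appropriately defined categories (Table 3"), and its Table 3 has the same upper limits, ">110 >160 >100". Neither table shows signs of redaction.

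For ECGs the SAP goes further: "The number of subjects with absolute ECG values and changes from baseline in the ranges shown in" its Table 6 is tabulated by visit. Table 6 includes heart-rate change (20 and 30 bpm or more), PR change (15% and 25% or more) and QTcF change (bands at 30 and 60 msec). SAP 8.4 gives hematology and chemistry shift tables relative to the normal range.

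Vital signs are among the primary endpoints (SAP 3.2.1), and the first-listed event of special interest in SAP 8.1.1 is "Supine Hypertension".

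**The concern.** An absolute limit says where a reading ended, not how far it moved. A subject already near 160 mmHg at baseline can be counted after a trivial change, and a subject who starts low can rise a long way without being counted. In a long-term safety study of a drug for which supine hypertension is an event of special interest, a reader will want to know how many subjects had a large rise. The plan answers that kind of question for QTcF, PR and ECG heart rate, but not for blood pressure.

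The remaining outputs answer it only in part. The by-visit summary gives the distribution of change but no number of subjects. The adverse-event tables include a blood-pressure reading only if it came with signs or symptoms or the investigator judged it clinically significant (protocol 7.2).

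**Working it through.** The plan states no figure on this point to reproduce. The check applies the Table 5 limits, then sizes the gap under stated assumptions.

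**1. The example (chosen for illustration).** Systolic 158 mmHg after a rise of 45 mmHg gives a baseline of 158 − 45 = 113 mmHg. Neither 113 nor 158 is below 85 or above 160, so no category and no flag applies. A move from 159 to 161 mmHg, a change of 2 mmHg, is counted.

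**2. How large a change can go uncounted.** To be counted, a rise must exceed 160 − baseline:

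| Baseline SBP (mmHg) | Rise must exceed (mmHg) |
|---|---|
| 100 | 60 |
| 113 | 47 |
| 130 | 30 |
| 150 | 10 |

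The largest swing that stays inside the limits is 160 − 85 = 75 mmHg systolic and 100 − 45 = 55 mmHg diastolic.

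**3. How many subjects might rise by 30 mmHg or more at a visit.** Assumptions not in the documents: change is normal with SD σ of 15 or 20 mmHg and mean shift μ of 0 or +8 mmHg. The 30 mmHg cut-point is also an assumption. P(rise ≥ 30) = 1 − Φ((30 − μ)/σ) and P(fall ≥ 30) = Φ((−30 − μ)/σ). The last column multiplies P(rise ≥ 30) by the 110 enrolled (SAP section 2).

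| μ | σ | (30 − μ)/σ | P(rise ≥ 30) | P(fall ≥ 30) | Expected risers of 110 |
|---|---|---|---|---|---|
| 0 | 15 | 2.00 | 2.3% | 2.3% | 2.5 |
| 0 | 20 | 1.50 | 6.7% | 6.7% | 7.3 |
| +8 | 15 | 1.47 | 7.1% | 0.6% | 7.8 |
| +8 | 20 | 1.10 | 13.6% | 2.9% | 14.9 |

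Because 110 is total enrolment, numbers at any one visit may be smaller.

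**4. How many of those would end at or below 160 mmHg.** This needs a baseline mean m, which the documents do not give, and a baseline SD, taken as 18 mmHg. The share is the integral over d ≥ 30 of [density of change at d] × P(follow-up ≤ 160 given d), divided by P(rise ≥ 30). Two models were used:
- Equal SD of 18 at both times: given change d, follow-up has mean m + μ + (d − μ)/2 and variance 18² − σ²/4.
- Change independent of baseline: given d, follow-up has mean m + d and variance 18².

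Results for μ = +8, with ranges over σ = 15 to 20:

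| Baseline mean (mmHg) | Equal SD | Change independent of baseline |
|---|---|---|
| 125 | 76–78% | 41–47% |
| 135 | 53–56% | 23–27% |
| 145 | 28–33% | 10–13% |

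The uncounted share runs from about one tenth to more than three quarters, depending on inputs that the documents do not supply.

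**The case against.** The strongest case against is that nothing is lost and nothing contradicts the protocol. A reader might infer that the rising subject is counted nowhere. The documents do not support that. SAP 8.5 summarizes change at each visit; protocol 8.1 defines a continuous summary with SD, quartiles, minimum and maximum; and SAP section 6 lists all data by subject. A single extreme rise may well appear as the maximum. A 45 mmHg rise is also uncommon on the assumptions above: at a shift of +8 mmHg, P(rise ≥ 45) is 1 − Φ(37/15) = 0.7% to 1 − Φ(37/20) = 3.2%, or about 1 to 4 of 110. This objection stands; only the tabulated count is missing.

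A reader might also infer that a population with low standing pressure must have low baselines, so that most large rises escape. That does not follow. Vital signs are taken seated or supine (protocol Table 1, footnote b), and SAP 8.5 uses seated baseline values where an orthostatic test was done.

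Nor would a count of rises by itself measure the effect of starting TD-9855. Baseline is Study 0170 Visit 9 (SAP 6.2), after a randomized withdrawal period (SAP 7.5). It is on drug for some subjects and may be off drug for others, so a common +8 mmHg shift cannot be presumed. A seated baseline set against a supine follow-up would add a position effect, although protocol 6.4.3.6 asks for a consistent position. Showing rises beside falls removes neither problem.

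Finally, the stopping criterion and the limits are absolute levels, the events of special interest are queried at each visit (protocol 7.1.4), and ECG practice does not oblige the same format for blood pressure. Heart-rate change is already counted from ECGs in SAP Table 6. These points keep this an improvement to the plan, not an error in it.

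**Conclusion.** The concern holds in a limited form. SAP Table 5 cannot identify a large blood-pressure rise that ends at or below 160/100 mmHg, and no planned table gives the number or percentage of subjects with a large change. This follows from the limits alone and does not depend on the modelling. The SAP's own treatment of ECG changes shows that such a count fits its approach.

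The number of subjects affected is uncertain: about 2 to 7% rising by 30 mmHg or more at zero mean shift and about 7 to 14% at +8 mmHg, for an assumed change SD of 15 to 20 mmHg. The proportion of these that Table 5 would miss cannot be fixed without the baseline mean. The documents do not support saying that the data are lost, that most large rises would be missed, or that the SAP departs from the protocol.

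**What to change.** In SAP 8.5 and Table 5, before database lock:

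- Add counts and percentages of subjects by systolic and diastolic change from baseline, by visit through Week 26, when scheduled vital signs end. Systolic changes of 20 and 30 mmHg or more, with matching diastolic categories, would serve as an example; the sponsor should set and justify the final cut-points.
- Show rises and falls side by side, so that ordinary variability is visible in this single-arm study.
- Restrict the change to baseline and follow-up readings in the same position, and state how many subjects this excludes. The documents do not say whether position is recorded at each reading, so confirm this first.
- Show the counts overall and by previous treatment in the Study 0170 randomized withdrawal period, which SAP 7.5 already summarizes.
- Treat heart-rate categories as optional, given Table 6.

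The cost is SAP wording and some table rows. The change values are already derived (SAP 6.3.3), and no new measurements are needed. The drawbacks are that blood pressure is labile, so some subjects will cross a cut-point by chance, and that the split by previous treatment will leave small groups. SAP 6.1.3 already drops subgroup safety summaries because of sample size, so the split should be presented as descriptive context only.
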